1.0 OBJECTIVES

This will be a multi-center, open-label, randomized study that directly compares the use of cyclosporine and plasma exchange to corticosteroids and plasma exchange as the initial treatment of patients with thrombotic thrombocytopenic purpura. This study has the following objectives:

Primary Objective

1.1 To determine if cyclosporine given individually as an adjunct to plasma exchange decreases the rate of exacerbation in patients with TTP compared to corticosteroids given as an adjunct to plasma exchange.

Secondary Objectives

1.2 To compare the CSA and PE treatment arm to the corticosteroid and PE treatment arm with respect to:

- exacerbation rate within 30 days post-PE
- clinical response rate
- number of exchange procedures to achieve clinical response
- relapse rate (recurrent disease >30 days after last PE)
- safety data for CSA as an adjunct to PE.
- the effects of corticosteroids vs. cyclosporine on ADAMTS13 antigen, activity, and ADAMTS13 antibody concentration and inhibitor titers using serial measurements both during and after discontinuation of study drug
- the VWF multimeric patterns after initial therapy and throughout longitudinal follow-up between the two treatment arms
- the laboratory biomarker(s) that are prognostic for TTP exacerbation and the risk of relapse

2.0 BACKGROUND

2.1 Clinical Presentation and Therapy of TTP

There have been tremendous advances in our knowledge and understanding of the pathophysiology of TTP since Drs. Amorosi and Ultmann characterized the pentad of findings (fever, microangiopathic hemolytic anemia, thrombocytopenia, neurologic, and renal findings) in a 1966 review of all 271 previously reported cases.(1) Despite early attempts at therapy which included corticosteroids, splenectomy, and heparin, TTP was almost uniformly fatal with 90% of patients dying from the disease. Following observations of clinical improvement with plasma-based therapy, clinical trials soon demonstrated an 80-90% remission rate. (2) Rock et al reported one of the only randomized clinical trials in TTP and were able to demonstrate the superiority of

therapeutic PE over simple plasma infusion in the acute treatment of TTP.(3) Based upon this study, PE is considered the standard of care of acute TTP.

Despite the dramatic improvement in outcome with PE, complications related to the central venous catheter (infection, hemorrhage, and pneumothorax) and the plasma infusion (hypersensitivity, volume depletion, and transmission of infection) may be associated with significant morbidity and mortality. Howard et al recently updated their experience with PE for TTP at the Oklahoma Blood Institute, reporting roughly a third of patients experienced significant complications from PE and a 2.4% mortality rate.(4) More importantly, approximately 50% of patients with idiopathic or acquired TTP will suffer a recurrence of the disease after tapering plasma exchange, requiring repeated exposure to the risks of PE therapy.(5) These historical data were confirmed by our cohort study of corticosteroids and PE in which 60% of patients required the re-initiation of plasma-based therapy within 30 days of discontinuing PE therapy.(6)

2.2 Advances in the Pathophysiology of TTP

The earliest observations by Amorosi and Ultmann from post-mortem examinations described microthrombi in multiple organs of the body, including the heart, kidneys, adrenal glands, and the brain.(1) The etiology of the microthrombi was not known, but the findings were fitting with the clinical presentation and course of the patients. In 1982, Moake et al were able to demonstrate that some patients with TTP had unusually large multimeric forms of vWF, similar to those stored in vascular endothelial cells and platelets, but typically absent from normal plasma.(7, 8) Given the finding that these forms disappeared with the acute presentation of TTP and reappeared in patients after remission, it was hypothesized that these highly active multimers of vWF were central to the pathogenesis of the microthrombi seen in TTP. It was postulated that a vWF “depolymerase” was responsible for the conversion of unusually large multimers of vWF to the smaller multimers that are usually found in the circulation.(9) In this scenario, the unusually large multimers of vWF would spontaneously react with platelets resulting in the platelet thrombi in the microvasculature. It was also hypothesized that an antibody inhibitor of the “depolymerase” could account for the unusually large multimers seen in the plasma based upon reports of patients with chronic relapsing TTP being controlled with immunosuppressive therapy.(10) The subsequent identification of a specific protease(11, 12) that was shown to cleave purified human vWF as well as the finding that patients with TTP had deficiencies of protease function further strengthened the hypothesis. Furlan et al went on to describe both a familial form of TTP who had a constitutional deficiency, as well as a non-familial form due to an inhibitor of the vWF-cleaving protease.(13) This protease, now known as ADAMTS13, was recently purified and the gene localized to the long arm of chromosome 9.(14, 15)

2.3 ADAMTS13 Activity and Inhibitors in Idiopathic TTP

Initial reports correlating ADAMTS13 activity with the clinical diagnosis of acquired TTP showed greater than 70% of patients with idiopathic TTP to have a severe deficiency of protease activity (< 5%) with the majority having demonstrable antibody inhibitors of the

protease.(13, 16, 17) Autoantibody inhibitors of ADAMTS13 are now recognized to be central to the pathophysiology of idiopathic TTP, as well as patients with pregnancy associated TTP and TTP secondary to an autoimmune disease (SLE) (18, 19). Additionally, persistent or recurrent antibody inhibitors of ADAMTS13 have been associated with recurrences of TTP as well as a chronic relapsing form of the disease, giving more validity to the hypothesis of targeting the antibody inhibitor of ADAMTS13 (20-22). In their review of 142 consecutive patients with TTP from the Oklahoma TTP-HUS Registry, Vesely et al described an inverse relationship between ADAMTS13 activity and both exacerbations (recurrent thrombocytopenia requiring the resumption of PE less than 30 days from the cessation of PE) and relapses of TTP that was most striking in patients with a severe ADAMTS13 deficiency. (21) Of the 18 patients with a severe deficiency of the protease, all but one had a demonstrable antibody inhibitor. Therefore, although patients are able to achieve a clinical remission with PE, a persistent antibody inhibitor of ADAMTS13 likely is a factor contributing to higher rates of exacerbation and relapse in patients with idiopathic TTP. Similar data was reported by Zheng et al, showing that 3 of 4 patients with severe ADAMTS13 deficiency and high titer inhibitory antibodies had a chronic relapsing course of their disease.(23) In these 4 patients PE did not result in any detectable plasma ADAMTS13 activity or a consistent reduction in the inhibitor titer. It is important to note that the risk of relapse in patients with persistent inhibitors is not uniform, as not all patients with persistent inhibitors are destined to relapse.(24) Recent data has also suggested that a severe deficiency of ADAMTS13 protease function alone may not always be sufficient to trigger an acute episode of TTP.(25)

2.4 Immunotherapy of Idiopathic TTP

There is an obvious rationale for the role of immunosuppressive therapy in patients with idiopathic TTP, both as an adjunct to PE therapy as well as a prophylactic therapy preventing the recurrence of disease. In theory, PE would serve as a “supportive therapy”, physically removing the inhibitor and inducing remission, while at the same time allowing CSA, a “disease-modifying therapy”, time to exert its effect. An effective immunosuppressive therapy could inhibit the production of the antibody inhibitor of ADAMTS13, resulting in shorter courses of PE, decreased exacerbations and relapse rates, and decreased exposure to the potential risks associated with plasma based therapy. Many cytotoxic and immunosuppressive agents have been reported to be effective in relapsed and refractory TTP, including: corticosteroids, cyclophosphamide, vincristine, cyclosporine, and rituximab.(22, 23, 26-38) Unfortunately, there has been very little good, prospective data with which to accurately judge the effectiveness of a particular therapy without confounding factors. Rituximab has been reported to be effective in refractory TTP, as well as being effective as prophylactic therapy in patients with recurrent inhibitors and a chronic relapsing course of TTP.(22) Rituximab though may have significant drawbacks including the need for intravenous administration, the potential for infusional toxicity and infectious complications. The issue of the active removal of rituximab when combined with PE therapy also remains to be addressed. Advantages with both corticosteroids and cyclosporine include their ability to be

administered orally, and in the case of cyclosporine, the ability to be administered concurrently with PE without significantly affecting cyclosporine concentration.(39)

2.5 Corticosteroids

Corticosteroids are routinely been used and recommended(40) as an adjunct to PE, but until recently no prospective studies have addressed their efficacy as an adjunct to PE. Among the series of patients reported by Zheng et al, four patients with undetectable ADAMTS13 activity and high titer inhibitors of the protease were followed serially. Two were treated with corticosteroids as an adjunct to plasma exchange. Both showed no sustained improvement in ADAMTS13 activity or inhibitor titers during the follow-up period. Data from our prospective cohort study of corticosteroids as an adjunct to PE also showed that the addition of corticosteroids to PE did not reduce the exacerbation rate compared to historical data from the Oklahoma TTP registry where corticosteroids are not routinely used.(6, 21, 41)

2.6 Clinical Outcome- Concurrent Corticosteroids and PE as Initial Therapy

A total of 12 patients with idiopathic TTP were treated with corticosteroids and PE. Patients received prednisone at a dose of 1 mg/kg/day concurrently with daily plasma exchange therapy which was continued until remission was achieved (platelet count $>150 \times 10^9/\text{ul}$). PE was then tapered and discontinued with the prednisone tapered over the next 4 weeks. Ten of 12 patients achieved remission after a median of 6.5 daily exchanges, but exacerbations of TTP occurred in 6/10 (60%), comparable to the 50% exacerbation rate from the Oklahoma Blood Institute where steroids were not routinely used. (Table 1) More importantly, there was no significant improvement in ADAMTS13 activity at remission nor suppression of the inhibitor measured within a week of tapering PE. Given these data, we then began to study alternative forms of immunosuppressive therapy as an adjunct to PE.

Table 1.
Clinical and Laboratory Data From Steroid and Plasma Exchange-Treated Patients

Clinical Data	
Remission	10/12
Med. Days to Remission	6.5 (range, 4 to 10)
Exacerbation Rate	6/10 (60%)
Laboratory Data	
Med. Pre-Treatment ADAMTS13	<1% (range, <1 to 5)
Med. Remission ADAMTS13	4% (range, <1 to 72)
Med. Pre-Treatment Inhibitor (ug/ml)	632 (range 188 to 3,574)
Med. Remission Inhibitor (ug/ml)	788 (range 144 to 8,113)

3.0 Rationale for Concurrent Cyclosporine and Plasma Exchange in TTP

Cyclosporine has been reported to be effective in cases of relapsed or refractory TTP.(26, 30, 31, 33) Our group has published a series of 3 patients with early

recurrences of TTP treated with cyclosporine alone, without the need for plasma exchange or infusion.(42) In addition to the clinical improvement seen, all 3 patients had significant increases in ADAMTS13 activity and suppression of the autoantibody inhibitor that correlated with a clinical remission of their disease. The therapeutic effect of CSA is thought to be related to its ability to inhibit the activation of genes necessary for the B-cell “helper” function (IL-4 and CD 40 ligand) of T-cells and T-cell proliferation (IL-2) required for the sustained production of high-affinity antibodies and memory B-cells to perpetuate a significant and sustained antibody response.(43) There is also increasing evidence that CD4⁺/CD25⁺ T-regulatory cells may be important in the control of pathologic immune responses in autoimmune hematologic disorders such as autoimmune hemolytic anemia and immune thrombocytopenic purpura (44-47). Low dose therapy with cyclosporine has also been shown to promote the development of CD24⁺/CD25⁺ T-regulatory cells in an animal model, providing an additional rationale for the use of CSA concurrent with PE.

3.1 Concurrent Cyclosporine and PE for Exacerbations and Refractory TTP

Ten patients with exacerbations or refractory TTP after their initial therapy received CSA concurrent with the resumption of PE.(48) All 10 patients were treated with concurrent CSA (2-3 mg/kg in a twice daily divided dose) and PE. CSA was continued for a total of 6 months and then discontinued. Nine of the 10 patients achieved remission after a median of 11 daily exchanges (range, 5-45), with only 1/9(9%) suffering an exacerbation after tapering PE. Median follow-up for the entire cohort is 31 months (range, 12 to 41). Eight of the 10 patients maintained a continuous remission throughout the planned 6 months of CSA and then discontinued therapy.

3.3 Combined Analysis: ADAMTS13 Activity, Antigen and Inhibitor After Concurrent CSA and PE

Patients on both cohort studies (exacerbation/refractory study and upfront study) of CSA and PE were followed serially to study the effect of CSA on ADAMTS13 activity, antigen, and inhibitor concentration and correlated with clinical outcome data. Complete ADAMTS13 and inhibitor data obtained serially for all CSA and PE treated patients during and after the 6 month period of CSA therapy is shown graphically in Figure 1. Although not randomized, these data suggest that cyclosporine improved ADAMTS13 activity via the suppression of the inhibitory IgG antibody. Although it could be argued that the improvement in ADAMTS13 activity could have resulted from PE therapy, the significant delay before the improvement in the ADAMTS13 activity argue that the CSA resulted in the suppression of the inhibitory antibody and the improvement in ADAMTS13 activity. Furthermore, the gradual decline seen after the discontinuation of CSA also support the hypothesis that it was the CSA and not the delayed effect of PE that resulted in the steady improvement in ADAMTS13 activity seen in this cohort of patients.

[figure not shown]

Figure 1. Serial determinations of the mean ADAMTS13% activity and inhibitor concentration throughout clinical follow-up both during and after therapy with cyclosporine. The arrow at the top of each graphs represent the duration of therapy with cyclosporine.

4.0 Toxicity of Combined Analysis of CSA and PE

Overall therapy with concurrent CSA and PE was well tolerated. Two patients treated with concurrent cyclosporine and PE had increases of the serum creatinine to 1.5 mg/dl

(normal < 1.4 mg/dl) after two and 4 weeks of cyclosporine therapy; both patients had their dose of cyclosporine decreased by 50% with subsequent normalization of the serum creatinine. Although this was presumed to be related to the cyclosporine, the concentrations of the drug obtained at the same time were not above the therapeutic range, raising the possibility that this mild increase in the serum creatinine may be related to the renal effects of TTP. Mild gastrointestinal toxicity was transiently experienced by 2 patients as well but did not require a decrease in the dose or frequency of the CSA therapy

5.0 Patient Selection

5.1 Inclusion of Women and Minorities.

Entry to this study is open to both men and women ages 18 and older, of all racial and ethnic subgroups. This study will be conducted in accordance with the International Conference on Harmonisation and the Helsinki Guidelines.

5.2 Eligibility Criteria.

- 5.2.1 Patients with a clinical diagnosis of idiopathic TTP as defined by a microangiopathic hemolytic anemia and thrombocytopenia ($<100 \times 10^3$)
- 5.2.2 Additional components of the pentad (fever, renal and neurologic abnormalities) need not be present.
- 5.2.3 Additional explanations for the microangiopathic changes including DIC and malignancy should be excluded.
- 5.2.4 Patients with pregnancy associated TTP will be permitted on this therapeutic trial if the child is delivered prior to the initiation of therapy for TTP. However, female patients that are breastfeeding and are unwilling to discontinue breastfeeding at the time of enrollment will be excluded from this study (see section 5.3.5)
- 5.2.5 Patients with a previous diagnosis of TTP are eligible to be enrolled provided they meet eligibility criteria and have not been treated for TTP in the past 30 days.
- 5.2.6 Given the potential for nephrotoxicity with CSA, all patients must have a serum creatinine of ≤ 2.5 mg/dl prior to enrollment

5.3 Exclusion Criteria.

- 5.3.1 In light of concern for the prompt initiation of PE, all patients with suspected TTP may be enrolled on this trial. If it is subsequently found that the patient does not meet enrollment criteria, they will be removed and their spot replaced for study purposes. Patients removed from the

study after enrollment will continue to be followed longitudinally for 6 months to be monitored for safety and will be included in the safety database.

- 5.3.2 Patients with TTP clinically categorized as secondary to stem cell transplant and solid organ, bloody diarrhea associated, malignancy associated, and drug associated will not be enrolled on this therapeutic study.
- 5.3.3 Incarcerated patients will be excluded from the study due to the inherent difficulties in maintaining close follow-up for study purposes in patients who are incarcerated.
- 5.3.4 Any patients already being treated chronically with corticosteroids or cyclosporine and taking these at the time of their presentation will be excluded from this study.
- 5.3.5 Female patients that are pregnant or breastfeeding and are unwilling to discontinue breastfeeding at the time of enrollment will be excluded from this study
- 5.3.6 Patients taking any medications contraindicated in combination with CSA that cannot be safely discontinued will be excluded from this study. A complete list of contraindicated medications is provided in Appendix 4.

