5.4 ENROLLMENT/REGISTRATION OF PATIENTS

- 5.4.1 Patients must give written, informed consent prior to enrollment on this study. Informed consent may be obtained by the protocol chairman, the principal investigator at one of the additional sites, or one of their designees.

It is not uncommon for patients to have mental status changes related to their diagnosis of TTP (typically reversible with therapy) that may prevent them from being able to provide informed consent. If the principal investigator, co-investigator, or research study nurse do not feel the patient is able to provide informed consent, the study consent may be signed by the patient's legally authorized representative to enroll the patient in the study.

If the patient's legally authorized representative signs the consent, the patient must be then re-consented with the "re-consent form" if/when the patient regains the ability to provide informed consent.

- 5.4.2 Given concerns for the need to rapidly initiate, PE therapy should not be withheld while awaiting enrollment to this study. To allow sufficient time to evaluate for eligibility and obtain informed consent, patients will be permitted to be enrolled within 48 hours after the first PE procedure.

5.4.3 At the time of enrollment on this protocol, patients must be registered by phone with the study coordinating office at Ohio State University, the lead institution for this study. Contact information for all study personnel, protocol chairman, and co-investigators is detailed in section 15.0 of the protocol.

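### Section 5.3.1 lets randomised patients be removed and replaced on a diagnosis made after arm and response are known, and Section 14 does not say how they are analysed

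*Combined protocol and SAP*

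**What the plan says.** Section 1.0 describes an open-label randomised study, and 6.1 randomises at registration. To avoid delaying plasma exchange, 5.3.1 admits anyone with suspected TTP and then says: "If it is subsequently found that the patient does not meet enrollment criteria, they will be removed and their spot replaced for study purposes". Anyone removed under this rule has therefore already been randomised. The only stated fate of such patients is to be "followed longitudinally for 6 months to be monitored for safety and will be included in the safety database".

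Several eligibility criteria carry a date:
- 5.2.5 asks that earlier TTP patients "have not been treated for TTP in the past 30 days".
- 5.2.6 sets a creatinine limit before enrollment.
- 5.3.4 concerns patients on chronic steroids or cyclosporine and "taking these at the time of their presentation will be excluded from this study".
- 5.3.5 covers women "unwilling to discontinue breastfeeding at the time of enrollment will be excluded from this study".

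The diagnostic criteria are looser. Section 5.2.3 reads "Additional explanations for the microangiopathic changes including DIC and malignancy should be excluded", and 5.3.2 lists categories including "bloody diarrhea associated, malignancy associated, and drug associated will not be enrolled on this therapeutic study".

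On timing of entry, 5.4.2 says: "To allow sufficient time to evaluate for eligibility and obtain informed consent, patients will be permitted to be enrolled within 48 hours" of the first exchange. Section 9.1.1 takes the smear, coagulation tests and direct antiglobulin test at enrollment.

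Sections 8.2.1 and 8.3.1 keep patients who do not reach remission, and refractory patients, on protocol; 8.3.1 scores refractory patients as failures. Section 14.2 compares success rates by arm without naming an analysis set. Its one explicit inclusion statement concerns the 12 internal-pilot patients and logistical problems.

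**The concern.** Refractory status is declared after one week, when the treating team knows both the arm and the course. Poor response is a natural prompt to look for another diagnosis. If the search finds, say, a malignancy or a drug cause, 5.3.1 removes and replaces the patient, while 8.3.1 would have counted the same patient as a failure. Nothing says which rule prevails, sets a deadline, or asks for the decision to be made without knowledge of arm and response.

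Removal could then depend on outcome. If it happened more in one arm, the comparison would favour that arm. If it happened equally, the test would roughly keep its size, but both success rates would be overstated to the extent that the removed failures were truly eligible. And because Section 14 is silent on removed patients, the denominator of the primary comparison could be settled after outcomes are known.

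**Working it through.** **The plan's own figure.** Inputs from 14.1: 50% v 80% success, two-sided 0.05, at least 80% power, 36 per arm. The unpooled normal formula gives n = (1.960 + 0.842)² × (0.50×0.50 + 0.80×0.20) / 0.30² = 7.849 × 0.41 / 0.09 = 35.76, so 36 per arm, with 80.3% power. The plan's 72 reproduces and contains no allowance for removals. The Mantel-Haenszel chi-square (unstratified, no continuity correction), enumerated exactly at 36 per arm, has 77.2% power.

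**Effect of relabelling failures.** The documents give no removal rate, so the fractions below are assumptions. Let p be the true success rate in both arms and f the fraction of an arm's failures re-diagnosed and replaced, with replacements exposed to the same process.
- Success rate among those retained: p / (1 − (1−p)f).
- Removals per 36 analysed: 36(1−p)f / (1 − (1−p)f).

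At p = 0.65:
- f = 0.1: 0.65/0.965 = 67.4%, 1.3 removals
- f = 0.2: 0.65/0.930 = 69.9%, 2.7 removals
- f = 0.3: 0.65/0.895 = 72.6%, 4.2 removals

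Exact enumeration of the same test at two-sided 0.05, 36 analysed per arm, ignoring the interim look:

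| f in one arm / other arm | two-sided error, p=65% | false superiority of first arm, p=65% | two-sided error, p=50% | two-sided error, p=80% |
|---|---|---|---|---|
| 0 / 0 | 4.8% | 2.4% | 4.5% | 4.9% |
| 10% / 0 | 5.3% | 3.9% | 5.0% | 5.3% |
| 20% / 0 | 7.1% | 6.3% | 6.9% | 6.5% |
| 30% / 0 | 10.6% | 10.2% | 10.7% | 8.7% |
| 20% / 10% | 5.5% | 4.1% | 5.1% | 5.5% |
| 30% / 20% | 5.7% | 4.4% | 5.3% | 5.7% |

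With equal relabelling of 10% to 30% in both arms, the two-sided error is about 4.9% at p = 65%, 4.4% to 4.5% at 50%, and 5.0% to 5.3% at 80%.

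**Cost of keeping everyone.** Suppose each arm is filled to 36 eligible patients, a fraction q of those randomised is ineligible, and all are analysed. At q = 10% the expected number per arm is 36/0.9 = 40. If ineligible patients succeed 50% of the time in either arm, the cyclosporine rate becomes 0.9×0.80 + 0.1×0.50 = 77%. Exact power falls from 77.2% to 75.0%, 72.2%, 69.2% and 66.1% at q = 5%, 10%, 15% and 20%. If all ineligible patients score as failures, it falls to 73.8%, 70.1%, 66.6% and 63.4%.

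**The case against.** The strongest reply is that the plan already contains most of the protection needed. Section 5.3.1 removes patients who fail enrollment criteria, and 5.3.2 says the listed categories are not to be enrolled, so the disqualifying fact is tied to enrollment and only its discovery is left open. DIC has enrollment tests. Sections 8.2.1 and 8.3.1 keep poor responders on protocol. Read naturally, removal, replacement and the safety database mean exclusion from efficacy. The documents give no mechanism for an arm difference, and at 10% relabelling in one arm the rise in type I error is about half a percentage point.

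Much of this stands. It would be too strong to say that the diagnostic criteria have no tie to enrollment. What remains is that 5.3.1 expressly permits a later finding, the 48-hour window in 5.4.2 limits entry and not removal, and nothing says that 8.3.1 prevails once a patient is re-diagnosed.

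Four stronger readings are tempting and not supported:
- A reader might infer that 14.2 contradicts 5.3.1 because it describes the primary interest as success among everyone treated. That remark contrasts the primary endpoint with the responder-only exacerbation analysis and does not address removals.
- A reader might infer very large inflation by supposing that 20% of one arm's randomisations are removed, all of them failures. At 65% success that is 0.20/0.35 = 57% of the arm's failures, which nothing in the documents suggests.
- A reader might want eligibility judged only on data collected by enrollment. That would keep patients whose malignancy or drug cause predated randomisation but was proven later, and would defeat the purpose of 5.3.1. Section 5.4.1 notes that altered mental status is not uncommon, so a history may well emerge late.
- A reader might expect an eligible-set analysis to be free of dilution. Ineligible patients who are never identified would still be in it.

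**Conclusion.** The concern holds as a gap in the rules, not as evidence of bias. Section 5.3.1 permits removal and replacement of randomised patients on diagnostic grounds after arm and response are known, and Section 14 does not say whether they count in the primary analysis. No passage shows that removal has depended on outcome or differed by arm.

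The size depends on assumed fractions. Type I error passes 6% in these scenarios only if relabelling reaches at least 20% of failures and falls in one arm only; that is about 2.7 removals per 36 analysed at 65% success. Modest arm differences leave it at 5.1% to 5.7% over success rates of 50% to 80%. Equal relabelling leaves it near nominal, with the reported success rate reading 67.4% to 72.6% instead of 65% if every removed failure was truly eligible, and less overstated where the re-diagnosis was correct. The sample size of 72 is not wrong on this ground.

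The point is worth acting on because the trial is small and open-label and the remedy is cheap.

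**What to change.** Amend 5.3.1 and 14.2 as follows.
1. Allow removal from the primary analysis only for a disqualifying fact that existed before randomisation, whenever it is discovered, by the same rule in both arms. Poor response, or a condition arising after randomisation, is not a ground. Where existing study personnel can do so, make the decision with arm and response withheld.
2. Record the 30-day outcome of removed patients within their existing 6-month follow-up. Report an all-randomised, as-assigned analysis beside the eligible-set analysis. State which is primary, and give one scoring rule for patients in whom TTP was ruled out.
3. Apply the rule to any patient already removed, and report removals with reasons and timing by arm. Section 14.2 says the internal-pilot accrual point has been reached, so this is a mid-trial change and is best made before the arms are compared.

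Replacement and prompt enrollment may continue.

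The cost is wording, a few outcome fields and one extra analysis. Masked review across sites could need extra staff, which is why it is asked for only where feasible. If the all-randomised set is made primary there is some dilution: at an assumed 10% ineligible with 50% success, exact power for 50% v 80% falls from 77.2% to about 72%.
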